313 to define different cutoffs for abnormal BMI and waist circumference, respectively, in Asian
314 populations.^{13,14} Second, waist circumference measurement includes both VAT and abdominal
315 subcutaneous adipose tissue (SAT) compartments. These two depots are anatomically and
316 physiologically distinct, especially within the obese population, and are differentially associated
317 with markers of cardiometabolic risk.¹⁵ VAT, but not abdominal subcutaneous fat, has been
318 shown to associate with incident T2D and pre-T2D¹⁶, incident hypertension¹⁷, and alterations in
319 left ventricular structure and function¹⁸, and has also been linked to increased risk of developing
320 ASCVD and cancer.¹⁹ Medical treatments that reduce VAT mass may translate into improved
321 major adverse cardiac event (MACE)-free survival.
322

323 Section 3: Liraglutide 3.0

324 *GLP-1: Physiology and current literature*

325 In response to a meal, GLP-1, an incretin hormone secreted from the L-cells in the lower gut,
326 stimulates endogenous insulin secretion in a glucose-dependent manner, decreases blood
327 glucagon levels, reduces gastric emptying and increases satiety. GLP-1 reduces appetite in
328 lean and normal weight individuals, as well as in obese individuals, and has been shown to
329 reduce body weight. The combination of these mechanisms makes GLP-1 receptor stimulation
330 an attractive mechanism to investigate for weight management.
331

332 *Liraglutide*

333 Liraglutide 3.0 mg (Saxenda®, Novo Nordisk, Bagsvaerd, Denmark) is a glucagon-like peptide
334 (GLP-1) receptor agonist indicated as an adjunct to a reduced-calorie diet and increased
335 physical activity for chronic weight management in adult patients with an initial body mass index
336 (BMI) of $\geq 30 \text{ kg/m}^2$ (obese) or in patients with a BMI of $\geq 27 \text{ kg/m}^2$ (overweight) in the presence
337 of at least one weight-related comorbid condition such as hypertension, type 2 diabetes mellitus,
338 or dyslipidemia.
339

340 Compared to human GLP-1, liraglutide has a C16 fatty (palmitic) acid chain attached at position
341 26 (lysine) of the peptide, and has lysine at position 34 replaced by arginine. When
342 administered subcutaneously, these structural modifications result in a compound with
343 protracted kinetic properties suitable for once daily injection. The dose approved for use in the

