631 **Imaging Assessments**

632 The primary and secondary endpoints of visceral fat, abdominal subcutaneous fat, lower body
 633 fat, liver fat, and total body fat and fat-free (lean) mass will be assessed using a Phillips 3T MRI
 634 system utilizing a two point Dixon fat-water segmentation technique (Advanced MR Analytics,
 635 Sweden).²¹ This MRI system has been extensively studied and validated in multiple cohorts,²¹⁻²³
 636 has excellent test/retest precision and reliability,²⁴ and is rapid (<6 minutes) and therefore cost
 637 effective.

638 **STATISTICAL CONSIDERATIONS:**

641 **Sample Size Calculation:**

642 This trial is powered to detect a clinically meaningful difference in the placebo-corrected relative
 643 reduction in VAT. The estimates used in the sample size calculations below are derived from

644 prior data from the SCALE program. Assuming a mean 8% relative reduction of VAT among
 645 placebo treated subjects and an expected 16% relative reduction of VAT among liraglutide
 646 treated subjects (with a standard deviation of 16%, based on data from [2]), we expect to require
 647 128 total subjects (in a 1:1 trial drug:placebo randomization scheme) to achieve 80% power to
 648 detect an 8% difference between groups at an alpha level of 0.05. Assuming an estimated 28%
 649 of subjects may withdraw trial medication during the trial, we expect a planned total of 178
 650 patients will be randomized in order to achieve at least 128 completers of the full trial protocol.
 651

Placebo-corrected Effect Size	Power		
	80%	85%	90%
Sample Size (Total N, 1:1 randomization)			
5%	322	368	432
8%	128	146	170
10%	82	92	108

652
 653 **Statistical Methods:** A formal statistical analysis plan will follow. Briefly, baseline
 654 characteristics between liraglutide and placebo treated groups will be compared using
 655 appropriate parametric or non-parametric tests depending on the distribution of the data. The
 656 primary outcome will be analyzed using an intention to treat analysis. Mean change in outcome
 657 measurements will be compared between groups using the appropriate statistical test.
 658 Outcomes will also be analyzed by subgroups including age (above/below median), sex, race
 659 (non-Hispanic black, non-Hispanic white, and Hispanic), BMI category (overweight, class I
 660 obese, class II/III obese), and prediabetes status (yes/no). In order to minimize type II error in

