 661 subgroup analyses by race, we will attempt to ensure Hispanics comprise at least 25% of the
 662 trial population. A pre-specified analysis stratified by those who did vs. did not lose $\geq 4\%$ body
 663 weight at 16 weeks of treatment will be performed prior to unblinding to determine differential
 664 outcomes among “responders” vs. “non-responders” as outlined in the package insert. All
 665 statistical tests are two-sided at a 5% significance level.
 666

667 **Interim Analysis:** No interim analysis will be performed.
 668

669 **Missing Data:** The preferred approach to missing data is to incorporate proactive standard
 670 operating procedures to mitigate the likelihood of missingness. We will implement measures to
 671 reduce missing data (both baseline and endpoint). The statistical analysis plan will describe
 672 analytical approaches to address missingness of data, including multiple imputation including
 673 the last observation carried forward (LOCF) and mixed-effects model repeated measure
 674 approaches. Sensitivity analyses will also be performed to determine the effect of missingness
 675 on the primary and secondary outcomes.
 676

DATA HANDLING AND RECORD KEEPING:

677 Subjects will be assigned an identification code. A subject's name and code will be contained
 678 within a small notebook and will be kept in a locked cabinet in the research coordinator's locked
 679 office. The research chart will contain personal health information and will be kept in locked file
 680 cabinet in the research coordinator's locked office. All other data on a computer will be de-
 681 identified with the subject's identification code. Blood samples waiting for analysis will not be
 682 labeled with the subject's name, but with the assigned identification code. The trial database will
 683 be password protected. No data will be sent over the internet unless it is encrypted. All email
 684 with subject-identifiable information will be password protected. Only key personnel will have
 685 access to the information in the trial database on an as-needed basis. Key personnel may not
 686

687 alter the data in the database or directly view all of it without specific cause and approval of the
688 PI.

689

690 **ETHICS:**

691

692 **Informed Consent**

693 Before screening takes place subjects will be provided with written and verbal information about

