1043 day of evaluation. If a result is outside the normal range, the Investigator will judge whether the
1044 abnormality is clinically significant or not. The signed laboratory report is retained at the
1045 Investigator site as source documentation. Any abnormal, clinically significant result identified at
1046 screening visit 1 will be recorded as a concomitant illness.

1047
1048 **Ascertainment of clinical safety endpoints**

1049 At each visit trial staff will review criteria for withdrawal and AEs/SAEs with the subject. There
1050 will not be external independent event adjudications for the adverse cardiovascular endpoints of
1051 death, MI or stroke. The Investigator will identify adverse cardiovascular events. These adverse
1052 events of interest include death, all cause and cardiovascular deaths, nonfatal myocardial
1053 infarction and nonfatal stroke. These will be defined prospectively and identified by the
1054 Investigator. These events will not undergo external independent event adjudication. These
1055 endpoints will be investigator identified using *a priori* criteria.

1056
1057 **Ascertainment of diet/physical activity**

1058 At each visit the trial staff will review diet and physical activity compliance with the subject.
1059 Subjects not meeting trial standards will be encouraged to adjust their behavior to adhere to trial

1060 requirements. Subjects not meeting requirements after 2 attempts at correction may be subject
1061 to withdrawal from the trial at the discretion of the Investigator.

1062

1063 **Subject Compliance:**

1064 At each visit the trial staff will review trial medication compliance with the subject. At the
1065 prescribed visits, the subject will return used or partly used trial products including all empty
1066 packaging materials. The investigator will assess the amount of return trial product and
1067 compare it to what was dispensed to estimate the subject's compliance with trial medication. If
1068 noncompliance is identified, the investigator will counsel the patient on the importance of trial
1069 medication compliance. Consistent failure to be compliant with trial medication or other trial
1070 protocols could ultimately lead to subject withdrawal from the trial.

1071

1072 **End of trial treatment strategy**

1073 Following the end of the treatment, all trial drug treatment will be discontinued and the trial drug

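### Discretionary withdrawal from the trial after randomisation for poor diet or activity adherence can differ by arm, and the week-40 recall only partly protects the intention-to-treat comparison

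*Protocol*

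**What the plan says.** Under Ascertainment of diet/physical activity, adherence is reviewed at every visit and those falling short are encouraged to improve. Then: "Subjects not meeting requirements after 2 attempts at correction may be subject" "to withdrawal from the trial at the discretion of the Investigator". Two other places give the same power in general terms. Item 2 of the Withdrawal Criteria covers subjects judged non-compliant with the protocol, and Subject Compliance says that consistent failure on trial medication or other trial requirements could end in withdrawal. Counseling on Diet and Physical Activity leaves the diet judgement to trial staff on review of food diaries, with no numerical threshold.

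On the drug's action, GLP-1: Physiology and current literature says that GLP-1 decreases "glucagon levels, reduces gastric emptying and increases satiety. GLP-1 reduces appetite in" lean, normal-weight and obese people.

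On analysis, Statistical Methods says the "primary outcome will be analyzed using an intention to treat analysis".

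On what happens after withdrawal, the protocol speaks in three places:

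- Subject Replacement says withdrawn participants will be asked back at the end of the trial period for imaging and laboratory tests and analysed by intention to treat.
- Visit Procedures asks for the Visit 16 procedures at premature withdrawal where possible. It adds Visit 16x, 40 weeks after randomisation, and provides for documenting a refusal to attend.
- Premature discontinuation, worded for a subject who chooses to stop early, offers end-of-trial imaging only if 40 weeks or more of treatment have been completed.

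The assessment schedule places MRI only at Visits 3 and 16.

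**The concern.** Before randomisation, adherence is a baseline characteristic and selecting on it is harmless to the comparison. The run-in exists for this: Visit 2 describes it as the period for judging adherence to the lifestyle advice. After randomisation, keeping a 500 kcal daily deficit is partly an outcome of treatment if the drug reduces appetite. Withdrawing people on that basis selects on a consequence of allocation. Blinding of the investigator does not prevent this, because any imbalance arises from the subject's behaviour and not from the assessor's knowledge.

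Two things are at stake. If withdrawn subjects are not scanned at week 40, their VAT outcome is missing for a reason related to both arm and outcome, and there is no intermediate MRI to draw on. If they are scanned, they have meanwhile lost the trial visits and counselling that both arms were meant to share, and trial treatment as well. The intention-to-treat estimate then includes the effect of an administrative withdrawal.

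**Working it through.** **The plan's own figure.** From Sample Size Calculation: mean VAT reduction 8% on placebo and 16% on liraglutide, SD 16, 1:1 allocation, 80% power to "detect an 8% difference between groups at an alpha level of 0.05"; Statistical Methods makes tests two-sided. A two-sample t-test needs 64 per arm, 128 in total, with power 80.1% (80.7% by the normal approximation). Allowing for 28% withdrawal, 128 / 0.72 = 177.8, so 178; in reverse, 178 × 0.72 = 128.2. Both figures reproduce. The 28% is not split by arm or by reason.

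**What the documents do not give.** They give no rate of adherence withdrawal, overall or by arm, and no relation between adherence and VAT change. The rest of this working is therefore illustration under stated assumptions.

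**Case 1: withdrawn subjects are not scanned, and only the remainder are compared.** Assume those lost have a VAT reduction 8 points worse than their own arm's mean. Losing a fraction p raises the mean reduction of those who remain by 8 × p / (1 − p):

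- p = 5%: 8 × 0.05 / 0.95 = 0.42
- p = 10%: 8 × 0.10 / 0.90 = 0.89
- p = 20%: 8 × 0.20 / 0.80 = 2.00

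The observed difference is 8 minus the placebo shift plus the liraglutide shift. Power is by the normal approximation at 64 per arm with SD 16, where the standard error is 16 × √(2/64) = 2.83.

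| Placebo lost | Liraglutide lost | Observed difference | Power |
|---|---|---|---|
| 5% | 5% | 8.00 | 81% |
| 10% | 5% | 8 − 0.89 + 0.42 = 7.53 | 76% |
| 20% | 5% | 8 − 2.00 + 0.42 = 6.42 | 62% |
| 5% | 10% | 8 − 0.42 + 0.89 = 8.47 | 85% |

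**A second model as a check.** Suppose the fraction w with the worst adherence is removed from each arm, and adherence has correlation ρ with VAT change. The shift is ρ × 16 × φ(z) / (1 − w), where z is the normal quantile at 1 − w and φ is the normal density.

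| Placebo / liraglutide lost | ρ = 0 | ρ = 0.3 | ρ = 0.5 |
|---|---|---|---|
| 5% / 5% | 8.0 | 8.0 | 8.0 |
| 10% / 5% | 8.0 | 7.6 | 7.3 |
| 20% / 5% | 8.0 | 6.8 | 6.1 |
| 5% / 10% | 8.0 | 8.4 | 8.7 |

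The two models agree in order of size. Both give no bias when the losses are equal, and a larger observed difference when the imbalance is reversed.

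**Case 2: every withdrawn subject is scanned at week 40.** The missing-data bias is zero. If 5% to 10% of liraglutide subjects had stopped treatment and lost the whole 8-point benefit, the arm mean would fall by 0.05 × 8 = 0.4 to 0.10 × 8 = 0.8 points at most. Withdrawn placebo subjects also lose visits and counselling, which pushes the other way, so the net sign is not determined.

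**How well the recall is secured.** Subject Replacement and Visit Procedures bring withdrawn subjects back for imaging. Premature discontinuation conditions imaging on a treatment duration that someone stopping early cannot have reached. That paragraph is worded for subjects who choose to stop, not for those the investigator withdraws. But Subject Replacement and Visit 16x cover both kinds, so the passages conflict for the first kind and leave room for doubt about the second. A scan taken at the time of withdrawal is not a week-40 value.

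**The case against.** The strongest reply is that nothing shows the rule would do harm. It is permissive, applies only after two corrective attempts, and is operated by a blinded investigator. Withdrawal is not exclusion: the protocol recalls these subjects at week 40, asks for Visit 16 procedures at withdrawal, and analyses by intention to treat. Missing Data plans imputation, mixed models and sensitivity analyses, so a bare comparison of those remaining is not the stated primary analysis. The 28% allowance may already cover these losses. All of this stands, except that analysis methods cannot recover a scan never taken, and blinding does not stop an imbalance that works through appetite.

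A reader might infer that the rule removes more placebo subjects and so understates the drug's effect. The protocol does not support that as a finding. The appetite text bears on diet, not on the 150-minute activity target. Tolerability and Adverse Events reports nausea in 47.6% of patients on liraglutide 3.0 mg in an earlier trial, which could hamper adherence in that arm. The only food diary described is kept between Visits 2 and 3, before randomisation, so it is unclear how far judged adherence would reflect appetite on drug.

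It can also be said that withdrawal stops trial drug, which is a matter of clinical management. That is why the point is limited to follow-up and outcome collection. Item 1 of the Withdrawal Criteria already separates withdrawal from follow-up from withdrawal of medication.

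**Conclusion.** The point holds as a risk, not as a demonstrated distortion. The protocol permits withdrawal from the whole trial after randomisation on a criterion that treatment can influence, without a threshold, and its safeguard is incomplete: attendance can be refused, the imaging provisions conflict, and there is no intermediate MRI.

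The size cannot be computed from the document. If non-returners are 8 points worse than their arm's mean and only the remainder are compared, the observed difference falls by about 0.5 of 8 points at 10% placebo against 5% liraglutide, and by about 1.6 at 20% against 5%. It rises by about 0.5 if 5% and 10% are lost instead. It is unbiased by missing data if losses and deficits are equal across arms, if adherence is unrelated to VAT change, or if every withdrawn subject is scanned at week 40.

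Neither the sample size nor the choice of intention to treat is wrong on this point. The change is worth making because the rule works against the analysis the protocol has chosen and the remedy uses visits already scheduled.

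**What to change.** In Ascertainment of diet/physical activity, Subject Compliance and item 2 of the Withdrawal Criteria, state that diet or activity non-adherence is not a ground for withdrawal from trial follow-up. Such subjects continue to be counselled, have adherence recorded at each visit, and stay on the visit schedule through the week-40 MRI. Editing the first section alone would leave the same power in the other two.

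Use lifestyle adherence as a gate only at the end of run-in, before randomisation, and afterwards only to define the per-protocol analysis.

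Reconcile the imaging condition in Premature discontinuation with Subject Replacement and Visit Procedures, so that it is clear who is to be scanned at week 40.

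Leave safety withdrawals, the subject's right to withdraw, and the investigator's decisions on stopping trial drug as they are.

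The cost is wording in three places and one reconciliation. The visits, counselling and week-40 scan are already planned for every randomised subject. The downside is that poorly adherent subjects remain in the data, which is what intention to treat requires. Some will still decline to attend, so the risk is reduced, not removed.

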 563 9. Current or history of treatment with medications that may cause significant weight
 564 gain, within 1 month prior to screening for this trial, including systemic corticosteroids
 565 (except for a short course of treatment, i.e., 7- 10 days), tri-cyclic antidepressants,
 566 atypical antipsychotic and mood stabilizers (e.g., imipramine, amitriptyline,
 567 mirtazapine, paroxetine, phenelzine, clorpromazine, thioridazine, clozapine,
 568 olanzapine, valproic acid and its derivatives, and lithium).
 569 10. Diet attempts using herbal supplements or over-the-counter medications within 1
 570 month prior to screening for this trial.
 571 11. Current participation in an organized weight reduction program or within the last 1
 572 month prior to screening for this trial.
 573 12. Participation in a clinical trial within the last 3 months prior to screening for this trial.
 574 13. Familial or personal history of multiple endocrine neoplasia type 2 or familial
 575 medullary thyroid carcinoma.
 576 14. Personal history of non-familial medullary thyroid carcinoma.
 577 15. History of Major Depressive Disorder within the last 2 years.
 578 16. History of other severe psychiatric disorders, e.g., schizophrenia, bipolar disorder.
 579 17. Any lifetime history of a suicide attempt.
 580 18. A history of any suicidal behavior in the last month prior to randomization.
 581 19. Surgery scheduled for the trial duration period, except for minor surgical procedures,
 582 at the discretion of the Investigator.
 583 20. Known or suspected hypersensitivity to trial product(s) or related product(s).
 584 21. Known or suspected abuse of alcohol or narcotics.
 585 22. Language barrier, mental incapacity, unwillingness or inability to understand.
 586 23. Females of childbearing potential who are pregnant, breast-feeding or intend to
 587 become pregnant or are not using adequate contraceptive methods. These include
 588 abstinence and the following methods: diaphragm with spermicide, condom with
 589 spermicide (by male partner), intrauterine device, sponge, spermicide, Norplant®,
 590 Depo-Provera® or oral contraceptives.

591

592 **Withdrawal Criteria:**

593 1. Participants may withdraw at will at any time.
 594 - Informed consent may be withdrawn at any time.

595 - Permission to follow up for endpoint determination may be withdrawn at any time
 596 - This is distinguished from withdrawal of trial medication.

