597 2. Participants can be withdrawn from the trial at the discretion of the Investigator due to
 598 safety concerns of if judged to be non-compliant with the trial protocol.

599 3. Pregnancy or intention of becoming pregnant

600 4. If target treatment dose of the randomized product is not tolerated by the subject.

601 5. If the trial investigator suspects acute pancreatitis, the trial drug will be discontinued until
 602 the confirmatory tests (clinically indicated laboratory and imaging) have been conducted
 603 and appropriate treatment has been administered. We anticipate confirmation within 72
 604 hours. If acute pancreatitis is confirmed, the participant will be withdrawn from the trial.
 605 If acute pancreatitis is not confirmed, the participant will resume the trial drug at the
 606 same dose previously used before temporary discontinuation.

607 6. Temporary trial drug discontinuation criteria:
 608 - Side effects to trial medication (until such side effects have resolved or have
 609 been otherwise addressed)
 610 - Acute illness requiring treatment or hospitalization
 611 - The longest time that the subject can be off trial drug and still continue in the trial
 612 is 4 weeks. If the trial drug is discontinued for >72 hours, then the dosing
 613 escalation regimen will be restarted at 0.6 mg daily and titrated up according to
 614 prescribing information recommendations.

616 **Subject Replacement**

617 Participants will not be replaced if they withdraw or become ineligible but they will be asked to
 618 return at the end of the trial period to complete the follow-up imaging/laboratory testing and
 619 analyzed in an intention to treat analysis. As up to a 28% drop-out rate is anticipated, enrolment
 620 will account for expected drop-out to minimize loss to follow-up given that subjects will not be
 621 replaced.

623 **Rationale for Trial Population**

624 The trial population represents the target population for which liraglutide is approved for chronic
 625 weight management in adult patients, with the additional inclusion criterion of a diagnosis of
 626 metabolic syndrome. This important criterion has been selected to enrich the trial population
 627 with participants with a high visceral adipose tissue burden in order to improve the statistical
 628 power to observe a meaningful effect on visceral adipose mass and enrich the trial population
 629 with individuals at high risk for cardiovascular disease.

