809 Background medication should be withheld on the day of the fasting Visits 1, 3, and 16 until
 810 blood sampling has been done. At all other visits the background medication and trial product
 811 should be taken as usual during the conduct of the trial.

812

813 Trial product will be dispensed at visits 3 through 15. Subjects will be asked to bring all empty,
 814 partly used and unused trial product at visits 4 through 16 for drug accountability. The
 815 computerized randomization system should be contacted for trial product dispensing. If the
 816 subject attends the clinic for a visit not described in the protocol, then an Unscheduled Visit
 817 Form must be completed. The Unscheduled Visit Form should not be completed if the sole
 818 purpose of the visit is trial product dispensing. If an unscheduled visit is made for the purpose of
 819 dispensing trial products to the subjects then an unscheduled dispensing session must be
 820 completed in the computerized randomization system. If it is not possible to attend the visit
 821 within the visit window, the subjects should be called in for an Unscheduled Visit.

822

823 In case a subject is being prematurely withdrawn from the trial before or at visit 16, the
 824 Investigator will ensure that the procedures for the End of Treatment visit (Visit 16) are

825 undertaken, if possible. The primary reason (adverse event, non-compliance with protocol or
826 other) for discontinuation will be specified in the CRF and a computerized randomization system
827 withdrawal session should be completed. Even if the subject is not able to attend a final visit, the
828 End of Trial Form (EOT) must be completed.

829
830 Subjects that have discontinued the trial prematurely before Visit 16 will be asked to attend a
831 visit (Visit 16x) taking place 40 weeks after the randomization date. The purpose of this visit will
832 be recording of all outcome assessments if possible. If the subject is not willing to attend Visit
833 16x, it should be documented in the patient medical record that the subject has refused to
834 attend the visit.

835
836 **Visit 1**
837 At Visit 1, the informed consent will be reviewed again for signature and participants will be
838 screened for eligibility in the trial. This will include interview assessment for inclusion and any
839 exclusion criteria and laboratory components of the metabolic syndrome. Subjects that meet all

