1074 collected. Subjects will be advised with regards to the best possible post-trial treatment options
1075 for their weight management and metabolic syndrome. These treatments will be at the
1076 discretion of the local Investigator. Unblinding will occur at LPLV and after ascertainment of
1077 primary and secondary endpoints.

1078

1079

1080 **Premature discontinuation**

1081 If the trial subject opts for early trial termination, he/she will be asked to attend a premature trial
1082 discontinuation visit at the time of discontinuation. The purpose of this visit will be to assess
1083 body weight, occurrence of AEs and discuss end of trial imaging studies. The PI will offer end of
1084 trial imaging to assess for the primary and secondary efficacy endpoints if the subject has
1085 completed at least 40 weeks of trial treatment. Every effort will be made to assess for AE and
1086 SAEs during the trial for all patients including those prematurely withdrawing from the trial.

1087

1088 **TRIAL DRUGS AND MATERIALS:**

1089 Treatment with liraglutide or placebo will be blinded to the subjects and investigators throughout
1090 the trial.

1091

1092 **Trial medication(s) / devices(s)**

1093 The administration of liraglutide/ placebo will be as outlined above.

1094 The following trial products will be supplied by Novo Nordisk, Denmark.

- Liraglutide 6.0 mg/mL, 3 mL pen-injector for subcutaneous injection
- Placebo 3 mL pen-injector for subcutaneous injection

1095 Liraglutide will be available at a concentration of 6.0 mg/mL. Liraglutide and placebo will be
1096 supplied in a 3 mL pen-injector . Correct dosing is achieved by using the dose counter and the
1097 dose pointer to see how many mg to select. The subject will hear a "click" every time they turn
1098 the dose selector. The dose will not be set by counting the number of clicks the subject hears.
1099 Dosing with the liraglutide/ placebo pen-injector is controlled by turning the dose selector until
1100 the dose indicator shows the relevant dose (0.6, 1.2, 1.8, 2.4 or 3.0 mg, respectively or
1101 placebo). Therefore, the dose level (injection volume) of liraglutide or placebo is open labeled.

1102

1103

1104

1105

1106 Liraglutide or placebo is administered once daily by subcutaneous injections with the pen-
1107 injector, either in the abdomen, thigh or upper arm. Injections can be done at any time of day

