1167 temperature must be kept. Storage facilities will be checked frequently (at least once every
1168 working day).

1169
1170 No trial product(s) should be dispensed to any person not enrolled in the trial and the
1171 computerized randomization system should always be updated when dispensing trial product(s).
1172 Returned trial product(s) (partly used or unused including empty packaging material) must be
1173 stored separately from non-allocated trial product(s) until the monitor has performed drug
1174 accountability. The monitor will be responsible for retrieval of trial products from the site.
1175 Destruction of trial products will be done according to local laws and will be recorded on a
1176 Destruction Form, which will be signed by the person responsible for destruction, as agreed with
1177 the monitor.

1178
1179 **Randomization and Blinding**

1180 Trial participants and investigators will be blinded to treatment allocation throughout the trial.

1181

1182 **Randomization Scheme:**

1183 Participants will be randomly assigned using a computerized randomization code generated by
1184 UT Southwestern.

1185

1186 **Breaking of Blinded Codes**

1187 Blinding codes will be broken at the end of the trial. Blinding codes will only be broken before
1188 the end of trial if a subject develops a serious adverse event requiring knowledge of the
1189 treatment allocation. At such time, the subject will be considered to have completed the trial and
1190 will not undergo any further trial treatment but may be asked to undergo assessment of trial
1191 endpoints when feasible. Whenever a code is broken, the person breaking the code must print
1192 the Code Break Confirmation generated by the computerized randomization system, record the
1193 reason, and sign and date the document. If the subject should be withdrawn following a code
1194 break, a withdrawal session should be completed in the computerized randomization system.

1195

1196 **CONCOMITANT ILLNESSES AND MEDICATIONS**

1197 All concomitant illnesses and medications will be recorded in the CRF and assessed as AEs or
1198 not AEs. If a subject is prescribed a medication meeting criteria for withdrawal/exclusion, the
1199 subject will have the opportunity to decide whether to take such medication and withdraw from
1200 the trial or not take it and continue the trial.

SUBJECT SAFETY AND DATA MONITORING**ADVERSE EVENTS:****Definitions****Adverse Event (AE):**

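### The early-termination clause offers the week-40 MRI only to subjects who have finished 40 weeks of treatment, contradicting the unconditional week-40 follow-up elsewhere in the protocol

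*Protocol*

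**What the plan says.** Premature discontinuation applies to subjects who leave by their own choice: "If the trial subject opts for early trial termination, he/she will be asked to attend a premature trial" discontinuation visit. That visit covers body weight, adverse events and a discussion of imaging. The investigator then offers end-of-trial imaging for the primary and secondary endpoints if the subject has "completed at least 40 weeks of trial treatment".

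Other sections treat early leavers differently:

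- Subject Replacement: subjects who withdraw or become ineligible are asked to "return at the end of the trial period to complete the follow-up imaging/laboratory testing and" be analysed by intention to treat.
- Visit Procedures, at the time of withdrawal: the "Investigator will ensure that the procedures for the End of Treatment visit (Visit 16) are" carried out if possible. Those procedures include the MRI.
- Visit Procedures, at week 40: subjects who left before Visit 16 are asked to attend a "visit (Visit 16x) taking place 40 weeks after the randomization date. The purpose of this visit will" be to record all outcome assessments where possible.
- Withdrawal Criteria: "Permission to follow up for endpoint determination may be withdrawn at any time", followed by "This is distinguished from withdrawal of trial medication". Follow-up for endpoints is thus kept apart from staying on drug.
- Breaking of Blinded Codes: a subject whose code is broken "will not undergo any further trial treatment but may be asked to undergo assessment of trial" endpoints when feasible.

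**The concern.** The treatment period is 40 weeks (Trial type) and no trial drug is given after Visit 16 at week 40. A condition of at least 40 weeks of treatment therefore excludes nearly everyone the clause is written for. Only a subject who leaves between weeks 40 and 42, or within the 3-day visit window, could meet it.

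The primary endpoint is at stake. The assessment schedule and the Visit 3 and Visit 16 record lists place visceral fat by MRI at those two visits only. A subject handled under the clause has no post-baseline value. The full analysis set still keeps that subject if any efficacy endpoint, such as weight, was recorded after baseline. The intention-to-treat analysis would then rest on scans largely from completers, plus imputation. Last observation carried forward, named under Missing Data, would have only the baseline scan to carry, which means zero change. The analysis plan cannot recover a scan that was never offered.

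**Working it through.** **The text.** For one subject who opts out at, say, week 20:

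| Section | MRI at withdrawal | MRI at week 40 or end of trial |
|---|---|---|
| Premature discontinuation | discussed | offered if 40 weeks of treatment completed: not met |
| Visit Procedures | yes, if possible (Visit 16 procedures) | yes, if possible (Visit 16x) |
| Subject Replacement | not stated | yes, asked to return |

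Both columns conflict. The second decides whether the primary endpoint exists for this subject.

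**The protocol's own figures.** Inputs from Sample Size Calculation are a difference of 8 points, SD 16, two-sided alpha 0.05, 80% power and 28% withdrawal of medication. A two-sample t-test at 8/16 = 0.5 SD needs 64 per arm, 128 in total. Then 128/0.72 = 177.8, or 178 randomised. Both figures reproduce and neither is disputed.

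**How many subjects.** 0.28 × 178 = 49.8, so about 50 at most. The clause covers only those who opt out, and the protocol does not give that number. Half would be about 25 and a quarter about 12.

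**Possible bias (illustration).** Assume equal dropout in both arms, an 8-point effect in completers, no scans retrieved from the affected subjects, and stoppers who retain a share r of the effect.

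- All-randomised effect: 0.72 × 8 + 0.28 × 8 × r.
- Observed scans, all 50 unscanned: 8.
- Observed scans, 25 unscanned: (0.72 × 8 + 0.14 × 8 × r)/0.86.
- Baseline carried forward for all 50: 0.72 × 8 = 5.76.

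| r | All-randomised effect | 50 unscanned, observed | 25 unscanned, observed | Baseline carried forward, 50 |
|---|---|---|---|---|
| 1 | 8.00 | 8.00 (0%) | 8.00 (0%) | 5.76 (28% below) |
| 0.5 | 6.88 | 8.00 (16% above) | 7.35 (7% above) | 5.76 (16% below) |
| 0 | 5.76 | 8.00 (39% above) | 6.70 (16% above) | 5.76 (0%) |

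**Power if everyone is scanned.** With 89 per arm and SD held at 16, t-test power is 91%, 81% or 67% for r = 1, 0.5 or 0. Retrieving the scans therefore does not guarantee more power. It makes the estimate apply to all randomised subjects.

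**The case against.** The strongest reply is that the clause does not say that imaging is withheld otherwise and does not cancel Visit 16x. The paragraph describes a visit at the time of discontinuation, so the condition might limit imaging at that visit only, with the week-40 return still in force. Harm would then need staff to follow one sentence and ignore two others. This reading does not fit the text well. The clause speaks of end-of-trial imaging for the efficacy endpoints, and a conditional offer has no purpose if the scan is offered anyway. Even on this reading it conflicts with Visit Procedures, which asks for the Visit 16 procedures at withdrawal.

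Several limits do stand:

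- The loss is possible, not certain, because staff following the other two sections would still request the scan.
- The figure of 50 is a ceiling. The 28% refers to withdrawal of medication, while the clause concerns leaving the trial by choice.
- Subjects who do not tolerate the target dose are withdrawn by rule and fall under the sections that carry no condition. The link between lost scans and tolerability is therefore only partial.
- Planned power is not reduced, since the trial is sized on 128 completers.
- The single post-baseline time point for a repeated-measures model comes from the MRI schedule, with or without the clause.
- Breaking of Blinded Codes does not directly contradict the clause; it shows only that endpoint assessment after treatment has ended is foreseen.

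**Conclusion.** The clause is wrong as written. It sets a condition that practically no early stopper can meet, and it contradicts the week-40 follow-up in Subject Replacement and Visit Procedures. If followed, it removes the primary-endpoint scan from subjects whom the intention-to-treat analysis retains.

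The number affected is at most about 50 of 178 and probably smaller. Depending on the method and on the effect retained in stoppers, the resulting error runs from 39% overstatement (observed scans only) to 28% understatement (baseline carried forward), and it can be zero. These are ranges under the stated assumptions, not predictions: the protocol gives neither the number who opt out nor any effect in stoppers. This should be fixed, but it does not affect the sample size.

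**What to change.** In Premature discontinuation, delete the condition on completed weeks of treatment. State that every randomised subject who has not withdrawn permission for follow-up is offered the week-40 MRI and laboratory outcomes at Visit 16x, whether or not still on drug, in line with Subject Replacement and Visit Procedures. Reconcile Visit Procedures and Premature discontinuation on which assessments are done at the withdrawal visit. How any MRI taken at withdrawal enters the analysis can be left to the SAP.

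The cost is a one-sentence amendment plus alignment of the withdrawal-visit wording. The week-40 scans are already planned, so no procedure is added.
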